5 GENERAL STATISTICAL CONSIDERATIONS

5.1 General Principles

All continuous variables will be summarized using the following descriptive statistics: n (non-missing sample size), mean, standard deviation, median, quartiles and range (maximum and minimum). Where appropriate (e.g., immunogenicity), geometric means and corresponding 95% confidence intervals will be included. The number and percent of participants (based on the population sample size) of observed levels will be reported for all categorical measures. Where appropriate (e.g., immunogenicity and safety outcomes), 95% confidence intervals for the proportion of participants with an event will be included.

In general, all data will be listed, sorted by treatment and participant, and when appropriate by visit number within participant.

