3.2 STUDY SCHEMA

Group		Trivalent P2-VP8 Dose	N	-7 ^a to -1	0	7	28	56	84	89, 91, 93	168	224
A Adult	A1	30 µg	12	B(S,I)	X	B(S)	X, B(I)	X, B(I)	B(I)			F
		Placebo	3	B(S,I)	P	B(S)	P, B(I)	P, B(I)	B(I)			F
	A2	90 µg	12	B(S,I)	X	B(S)	X, B(I)	X, B(I)	B(I)			F
		Placebo	3	B(S,I)	P	B(S)	P, B(I)	P, B(I)	B(I)			F
A Total			30									
B Toddler	B1	30 µg	12	B(S,I)	X	B(S)	B(I)				F	
		Placebo	3	B(S,I)	P	B(S)	B(I)				F	
	B2	90 µg	12	B(S,I)	X	B(S)	B(I)				F	
		Placebo	3	B(S,I)	P	B(S)	B(I)				F	
B Total			30									
C Infant	C1	15 µg	12	B(S,I)	X	B(S)	X	X, B(I)	B(I)	Sh		F
		Placebo	4	B(S,I)	P	B(S)	P	P, B(I)	B(I)	Sh		F
	C2	30 µg	12	B(S,I)	X	B(S)	X	X, B(I)	B(I)	Sh		F
		Placebo	4	B(S,I)	P	B(S)	P	P, B(I)	B(I)	Sh		F
	C3	90 µg	12	B(S,I)	X	B(S)	X	X, B(I)	B(I)	Sh		F
		Placebo	4	B(S,I)	P	B(S)	P	P, B(I)	B(I)	Sh		F
C Total			48									
D Infant		15 µg	138	B(S,I)	X		X	X, B(I)	B(I)	Sh		F
		30 µg	138	B(S,I)	X		X	X, B(I)	B(I)	Sh		F
		90 µg	138	B(S,I)	X		X	X, B(I)	B(I)	Sh		F
		Placebo	138	B(S,I)	P		P	P, B(I)	B(I)	Sh		F
D Total			552									
All Cohorts Total			660									

X = Trivalent P2-VP8 vaccine

P = placebo

B = blood sample for (S) safety and/or (I) immunogenicity testing

F = final study f/u visit/call

Sh = stool samples to assess Rotarix shedding. Only at RMPRU (Soweto).

^aFor adult and toddler cohorts, -28 to -1

For each age group, progression from one dose level to the next will require review of clinical and safety lab data through 7 days after the first dose at the lower dose level. Safety laboratory blood specimens will be drawn at baseline for all participants (screening) and 7 days after first study injection in Groups A, B and C.

[figure not shown]
Blood samples for immunogenicity analysis will be obtained at baseline for all participants, Days 28, 56 and 84 for Group A (adults), Day 28 for Group B (toddlers), and Days 56 and 84 for Groups C and D (infants).

Stool samples to assess Rotarix shedding will be obtained from infants (Groups C and D) on days 89, 91 and 93 (i.e., 5, 7 and 9 days after the first Rotarix dose on day 84) in the subset of infants enrolled at the Respiratory and Meningeal Pathogens Research Unit (RMPRU).

For each dose level, progression from adults in Group A to toddlers in Group B and then to infants in Group C will require review of clinical and safety laboratory data through 7 days after study injection in the older group. (see Figure 1)

These determinations will be made by the Safety Review Committee (SRC).

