5.3.2 Safety Population

All participants in the enrolled population who receive a study vaccination and have safety data available will be included in the safety population. Treatment groups for safety analysis after a particular vaccination (1st, 2nd or 3rd) will be assigned according to the actual treatment received. For the analysis of accumulated safety data, participants will be grouped according to the first dose received and if a participant received mixed doses (e.g., 30 µg and 90 µg of P2-VP8 at Dose 1 & 2), the safety data collected after the start of the mixed dosing (e.g. post Dose 2) will be excluded. All excluded data will be presented in the data listings. All safety analyses will be performed using this population.

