5.3.3 Full Analysis (FA) Population (Modified Intent To Treat Population)

All participants in the enrolled population who were randomized, received a study vaccination, and have post-vaccination immunogenicity measurement(s). For the viral shedding analysis, the FA population will include the enrolled population who were randomized, received a study vaccination, and have any post-Rotarix shedding measurement(s). The analysis based on this population will serve as supportive results for the primary immunogenicity and viral shedding objectives. Participants will be analyzed as randomized.

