5.5 Missing Data

In general, all missing data will be treated as missing completely at random and no imputation will be performed except for the safety endpoints as described below. Non-analyzable data (e.g., due to major protocol violations) will be documented in the deviations.

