7.1.2 Tolerability

All local reactions and systemic reactogenicity reported up to 7 days post vaccination are included. To assess tolerability, the number and percentage of participants with Grade 2 or higher local or systemic reactions is tabulated by study cohort and by product received along with their corresponding 95% confidence intervals. Local and systemic reactions are tabulated separately. Overall summaries by cohort and by product received will include the number and percentage of participants experiencing: (1) each specific reaction at Grade 2 or greater after each injection; (2) each specific reaction at Grade 2 or greater after any injection; (3) any reaction at Grade 2 or greater after each injection; and (4) any reaction at Grade 2 or greater after any injection (**Table 14.3.1.1 for local** and **Table 14.3.1.2 for systemic**). Descriptive statistics will be used to summarize the duration of local and systemic reactions. In addition, local and systemic reactions will be summarized by grade.

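### SAP section 5.1 divides every categorical percentage by the population size, which understates per-injection reaction rates, supportive per-visit response rates and single-day shedding rates when some participants have no result

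*SAP*

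**What the plan says.** Section 5.1 (General Principles) sets the rule for percentages: "The number and percent of participants (based on the population sample size) of observed levels will be reported for all categorical measures". The sentence opening the same paragraph gives continuous measures a different basis, the non-missing sample size.

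The populations that this rule points to are defined in section 5.3:

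- **Safety (5.3.2):** "All participants in the enrolled population who receive a study vaccination and have safety data available will be included in the safety population". One vaccination is enough.
- **FA, immunogenicity (5.3.3):** some post-vaccination titer is required. Neither a result at every visit nor a baseline titer is required.
- **FA, shedding (5.3.3):** any one post-Rotarix shedding measurement is enough.
- **Per protocol (PP, 5.3.4):** all scheduled visits and vaccinations must be complete. For shedding, the added condition is one stool sample in the 5-to-9-day window.

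Several planned summaries concern a single injection, visit or day. Section 7.1.2 asks for "each specific reaction at Grade 2 or greater after each injection". Section 7.1.4 asks for response proportions by time point, and section 7.1.5 for shedding on each of Days 89, 91 and 93. None of these states a denominator.

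Section 5.5 says that "all missing data will be treated as missing completely at random and no imputation will be performed", and then makes an exception for safety endpoints.

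**The concern.** A percentage for one injection, visit or day describes those who were exposed or measured then. With population N below the line, anyone not exposed or not measured adds to the denominator and can never add to the numerator. This happens in three places:

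- **(a) Reactions after injections 2 and 3 (adults and infants).** Someone who stopped after injection 1 appears reaction-free at later injections. The vaccine then looks better tolerated on repeat dosing than it was.
- **(b) FA response rates by visit.** An infant with a Day 56 titer but no Day 84 titer is counted at Day 84 as a non-responder. So is a participant with no baseline titer, for whom the fold rise defined in section 2.3.4 cannot be computed.
- **(c) Shedding on a single day (FA and PP).** An infant who gave stool on another day is counted as not shedding on the missing day.

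For (b) and (c), the denominator has the effect of a negative imputation, and section 5.5 says that none is made. Two programmers could follow 5.1 and 5.5 respectively and produce different tables. The percentage can also rest on a different n from the logistic model reported beside it, since a model fitted to observed outcomes omits participants with no result. A response rate would likewise rest on a different n from the geometric mean titer for the same assay and visit.

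**Working it through.** **Inputs from the SAP**

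- Infants per dose group, Groups C and D combined: 12 + 138 = 150 (sections 3.2 and 4).
- Evaluable for immunogenicity: at least 90%, so 150 × 0.90 = 135 (section 4).
- Response rates used for power: 65% vs 80% and 60% vs 80% (section 4).
- Hypothesis benchmark: 60% responding to at least two of three strains (section 1.1).

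**The plan's own figure.** Section 4 states power of at least 74% and 95% (Fisher's exact, two-tailed, 135 per group). Full enumeration at two-sided 0.05 gives 75.3% for 65% vs 80% and 93.9% for 60% vs 80%. The pooled normal approximation gives 79.1% and 95.2%. The exact second figure is about one point under the stated one, which does not bear on this point. What matters is that the sample size rests on the 135 with data and not on the 150 in the group.

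**Effect of the 5.1 denominator**

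Reported rate = true rate × (n with data ÷ population N)

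The 2% and 5% missing fractions are assumptions. The 10% is the plan's immunogenicity planning figure. The 20% column is an assumed reaction rate.

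| Missing | n with data / N | 80% becomes | 60% becomes | 20% becomes |
|---|---|---|---|---|
| 2% | 147/150 = 0.980 | 78.4% | 58.8% | 19.6% |
| 5% (142.5 taken as 142) | 142/150 = 0.947 | 75.7% | 56.8% | 18.9% |
| 10% | 135/150 = 0.900 | 72.0% | 54.0% | 18.0% |

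**Clopper-Pearson 95% intervals at 10% missing**

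- Response 80%: 108/135 = 80.0% (72.3 to 86.4) against 108/150 = 72.0% (64.1 to 79.0).
- Response 60%: 81/135 = 60.0% (51.2 to 68.3) against 81/150 = 54.0% (45.7 to 62.2).
- Reaction after injection 3: 27/135 = 20.0% (13.6 to 27.7) against 27/150 = 18.0% (12.2 to 25.1).

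**True rate needed to report 60%:** 60 ÷ 0.980 = 61.2%, 60 ÷ 0.947 = 63.4% and 60 ÷ 0.900 = 66.7% respectively.

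**Where the rule changes little or nothing**

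- PP immunogenicity: PP requires all visits and vaccinations, so n with data is close to N.
- Primary safety endpoints (section 4.1.1): these are proportions with at least one event, for which population N is a usual denominator.
- Shedding on any of the three days, the main shedding summary in 7.1.5: every infant in the shedding FA population has at least one result, so N and n with data coincide.
- PP single-day shedding is not protected in the same way. The separate one-sample condition would be redundant if PP already required all three stools, so single-day gaps appear to be allowed.

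**The case against.** The best defence is that 5.1 is loose wording that nobody would program literally. For safety, section 5.3.2 says: "Treatment groups for safety analysis after a particular vaccination (1st, 2nd or 3rd) will be assigned according to the actual treatment received". Someone who never had injection 2 has no treatment received at injection 2 and so arguably belongs to no group in that table. Section 5.3 also speaks of excluding visits and observations as well as participants, and the table mock-ups are in a separate appendix. This has weight, but 5.3.2 is a rule for grouping and states no denominator, while 5.1 states one explicitly and contrasts it with the non-missing n. The plan should not depend on the programmer choosing the sensible reading.

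The defence is right on size. The 10% loss is the immunogenicity assumption; for safety, section 4 expects data from almost all participants. In the FA population, reaching 72% would require all 15 missing infants to have a titer at the other visit, because those with no post-vaccination titer are already excluded. FA immunogenicity is supportive, and shedding is exploratory.

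Four stronger readings are tempting, and the document does not support them:

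- **Never-sampled participants are counted as non-responders or non-shedders.** They are not: participants with no post-vaccination titer, or no shedding measurement, fall outside the respective FA populations.
- **Section 5.5 is contradicted for reaction rates too.** Section 5.5 exempts safety endpoints, although no description of that exemption follows there. The conflict can be claimed only for immunogenicity and shedding.
- **Infant laboratory percentages are heavily diluted**, because post-vaccination safety bleeds are taken only "7 days after first study injection in Groups A, B and C" and not in Group D. Section 7.1.3 plans a descriptive analysis of changes in values; no table of graded Day 7 results for pooled infants appears.
- **The comparison of doses is distorted by dropout after reactions.** This is possible, but no figure in the document bears on it.

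**Conclusion.** The point holds as a defect in a stated rule. Followed as written, section 5.1 biases low the reaction rates after injections 2 and 3, the supportive FA response rates at visits with missing results, and single-day shedding in both FA and PP. The direction is certain whenever results are missing; the size is the fraction missing. An 80% rate loses 1.6 percentage points at an assumed 2% missing, 4.3 at about 5%, and 8.0 at 10%, which is an upper illustration for FA and not an expected value.

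The main conclusions are not at risk. PP immunogenicity, the primary at-least-one-event safety endpoints and any-day shedding are little or not affected, so the 60% benchmark is exposed only in the supportive FA results. A reader might also infer a loss of power from the diluted rates. That would follow only if the tests themselves scored missing results as negative, which the plan does not say.

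**What to change.** Replace the parenthesis in section 5.1 with denominators by type of summary:

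- **After a given injection:** participants in the population who received that injection and have reactogenicity data for it.
- **At a given visit or day (response, shedding):** participants in the population with a non-missing result at that time point and, for any fold-rise response, a baseline titer.
- **At-least-one-event and disposition summaries:** the population N, as now.

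Print the n used in each table, so that the percentage, its interval and the model p-value can be seen to rest on the same participants.

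The cost is one sentence in the SAP and matching denominators in the table shells. No data collection or sample size changes. Some reaction rates after later injections will be slightly higher, and so less favourable to the vaccine, than under the literal rule.

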5.2 Timing of Analyses

The primary analysis of safety and immunogenicity data through 28 days (day 84) post-final vaccination and the analysis of shedding data from days 5, 7 and 9 post first Rotarix dose on day 84 will be performed when all relevant safety, immunogenicity and shedding data have been received, all associated data queries have been resolved and the only remaining data to be collected are long-term safety data. A copy of the database will be made at that time and 'frozen' for the primary analyses prior to final database lock. The final clinical study report (CSR) will include all the primary analyses (which will not be repeated) as well as all secondary and exploratory analyses. These will be performed once the study is completed (final visit is day 224 after the last enrolled infant) and the database has been cleaned and locked.

5.3 Analysis Populations

A tabular listing of all participants, visits, and observations excluded from the safety, full analysis and per protocol populations will be provided in the CSR (Appendix 16.2.3).

5.3.1 Enrolled Population

All screened participants who provide informed consent (IC), regardless of the participant's randomization and treatment status in the trial, will be included in the enrolled population.

5.3.2 Safety Population

All participants in the enrolled population who receive a study vaccination and have safety data available will be included in the safety population. Treatment groups for safety analysis after a particular vaccination (1st, 2nd or 3rd) will be assigned according to the actual treatment received. For the analysis of accumulated safety data, participants will be grouped according to the first dose received and if a participant received mixed doses (e.g., 30 µg and 90 µg of P2-VP8 at Dose 1 & 2), the safety data collected after the start of the mixed dosing (e.g. post Dose 2) will be excluded. All excluded data will be presented in the data listings. All safety analyses will be performed using this population.

5.3.3 Full Analysis (FA) Population (Modified Intent To Treat Population)

All participants in the enrolled population who were randomized, received a study vaccination, and have post-vaccination immunogenicity measurement(s). For the viral shedding analysis, the FA population will include the enrolled population who were randomized, received a study vaccination, and have any post-Rotarix shedding measurement(s). The analysis based on this population will serve as supportive results for the primary immunogenicity and viral shedding objectives. Participants will be analyzed as randomized.

5.3.4 Per Protocol Population

All randomized participants who adhere to the protocol, complete all their scheduled visits and vaccinations and present no major protocol violations prior to database lock. A “major” violation is defined as a protocol violation that is considered to have an impact on the immunogenicity results of the study. Volunteers are analyzed according to randomized treatment arm. For the viral shedding analysis, the per protocol (PP) population will include participants meeting all the above criteria with the addition that participants must have provided at least one stool sample between 5 and 9 days following the first dose of Rotarix.

The specific criteria for exclusion of participants from the PP population will be established before breaking the blind and will be based on the blinded review of protocol violations.

5.4 Covariates and Subgroups

There is no *a priori* plan to summarize the immunogenicity or safety endpoints for covariates. The protocol is set up as a descending age-group study, so each age-group will be summarized separately. The 3 age groups to be analyzed are adults (18-45 years), toddlers (2 to <3 years) and infants (6 to <8 weeks). Safety endpoints for infants will be presented for each site and for all sites combined.

5.5 Missing Data

In general, all missing data will be treated as missing completely at random and no imputation will be performed except for the safety endpoints as described below. Non-analyzable data (e.g., due to major protocol violations) will be documented in the deviations.

5.6 Interim Analyses and Data Monitoring

The primary analysis of safety and immunogenicity data through 28 days (day 84) post-final vaccination and the analysis of shedding data from days 5, 7 and 9 post first Rotarix dose on day 84 will be performed prior to final database lock (see Section 5.2). Review of all blinded safety data by the Safety Review Committee (SRC) occurs on a regular basis. The site PIs and/or designated site staff are responsible for continuous close safety monitoring of all study participants and for alerting the Sponsor if unexpected concerns arise or stopping criteria are met. The Emmes medical monitor is also automatically alerted via email as soon as any unexpected SAE or event contributing to any stopping criteria was reported.

5.6.1 Safety Review Committee

A SRC, comprised of the site PIs from each study site, the Sponsor medical officer, the Emmes medical monitor and two independent local medical experts, has monitored safety throughout the duration of the study (in addition to the Data Safety Monitoring Board described in section 8.2 of the protocol). The responsibilities and procedures of the SRC were defined in the SRC Charter. The study statistician with assistance of the data management staff prepares safety reports as needed for SRC discussions. In addition to routine review of safety information, a central role of the SRC was the review of safety data for the recommendation of whether to progress to the next dose level in each age cohort and to the next age cohort. Cumulative safety data are available continuously for review by SRC members, and safety reports are prepared for each SRC deliberation of dose escalation and progression to subsequent cohorts (adults to toddlers and toddlers to infants).

The SRC members review the safety data throughout the study to determine whether pause criteria had been met.

5.6.2 Study Pause

Study pause is defined as a decision to cease, temporarily or permanently, enrollment and all study injections. Study pause would not eliminate any safety follow-up procedures specified by the protocol. The Sponsor would pause the study if the SRC determined that study pause criteria had been met. The DSMB would be convened by teleconference to review study pauses and provide recommendations to the Sponsor regarding continuation or permanent discontinuation of study vaccinations, or study modification.

Meeting one or more of the following criteria would automatically pause or halt further study injections in the study. These pause rules refer to suspected adverse reactions across all cohorts, as defined below:

- One participant with a vaccine-related serious AE (SAE);
- Two participants with \geq grade 3 (severe) localized inflammatory reaction at the injection site;

- The same objective \geq grade 3 (severe) systemic reactogenicity signs or symptoms (fever, vomiting), within seven days following study injection in three participants in Groups A, B or C, and $\geq 5\%$ of participants in Group D;
- Two participants with a systemic rash, including, but not limited to, generalized urticaria, generalized petechiae, or erythema multiforme, within seven days following study injection;
- Two participants with the same \geq grade 3 (severe) vaccine-related abnormal clinical laboratory evaluation, within seven days following study injection.

5.7 Multicenter Studies

This study is being conducted at 3 sites: the Respiratory and Meningeal Pathogens Research Unit (RMPRU) in Soweto enrolled all participants in groups A to C. Group D infants were enrolled at 3 sites: RMPRU, SRC (Shandukani Research Centre) and FAM-CRU (Family Clinical Research Unit, Tygerberg). All summary tables, graphs and listings for infants in groups C and D will be reported by site and for all 3 sites combined.

5.8 Multiple Comparisons/Multiplicity

For each event/endpoint, a multiplicity adjustment for 4 treatment groups will be applied using a sequential testing approach by performing an overall comparison of all treatment groups prior to pairwise comparisons. No multiplicity adjustment for multiple immunogenicity endpoints is planned, since the dose selection for the Phase 3 will be based on comprehensive statistical and clinical evaluation of all immunogenicity endpoints including safety results.

